8.6.3 Analysis of secondary endpoints

All secondary analyses will be performed using the FAS, unless otherwise stated. Proportions in ASAS40 at Weeks 24 will be analyzed based on the CMH method described for ASAS20 in primary analysis. Due to the placebo group switching to 200 mg tildrakizumab at [REDACTED], the comparison between active drug and placebo will not be performed for the secondary endpoints collected after [REDACTED]. ASAS20 and ASAS40 up to [REDACTED] will be summarized with descriptive statistics.

Analysis on ASAS40 at [REDACTED] will also be performed for the PPAS.

8.6.4 Analysis of exploratory endpoints

The response-type endpoints (ASAS20/40 at other measurement time points, ASAS70, ASAS5/6 up to [REDACTED] and proportion of subjects who require adjustment of background therapy at Week 16 will be summarized with descriptive statistics. Continuous endpoints (change from baseline in PtGA of disease activity, Total Back Pain, Nocturnal Pain, Inflammation, BASFI, BASMI, BASDAI, ASQoL, ASDAS-CRP, ASDAS-ESR, MASES, SF-36, FACIT-fatigue, TJC46, SJC44, hsCRP, SPARCC MRI Index of Disease Activity Score of the SI Joints, SPARCC MRI Index of Disease Activity Score of the Spine, and Modified Berlin ASspiMRI) up to [REDACTED] will be analyzed based on a MMRM analysis that includes the fixed effects of treatment, visit, treatment by visit interaction, prior anti-TNF use (yes/no), and Baseline value. Due to placebo group switching to 200 mg Tildrakizumab at [REDACTED], the comparison between active drug and placebo will not be performed for the exploratory endpoints collected after [REDACTED]. Continuous endpoints after [REDACTED] be summarized descriptively.

Below is an example of the SAS code for the MMRM

[REDACTED]

For [REDACTED], the proportions of subjects who achieve ASAS20, ASAS40, ASAS70, and ASAS5/6, at each measured time point during [REDACTED] will be summarized by treatment

Statistical Analysis Plan (SAP)

group; change from Baseline in PtGA of disease activity, Total Back Pain, Nocturnal Pain, Inflammation, BASFI, BASMI, BASDAI, MASES, SF-36, FACIT-fatigue, TJC46, and SJC44 during Weeks 53 to 72 will be summarized descriptively by treatment group. In addition, there will be sub-groups of patients in Part 3 who either did or did not receive any new therapy for AS and these will be analyzed separately for ASAS20, ASAS40, and ASAS70.

All the exploratory analyses will be based on the FAS.

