Subjects randomized to receive tildrakizumab during Part 1 of both stages of the study who achieve ASAS20 at [ ] receive treatment with [ ] tildrakizumab [ ] until [ ]. Subjects receiving tildrakizumab during Part 1 [ ] will discontinue IMP treatment and enter the [ ]. Subjects randomized to receive placebo during Part 1 of both stages of the study who complete the Week 24 visit will continue to Part 2 and receive tildrakizumab [ ] until [ ] even if they do not achieve ASAS20. Subjects discontinued from IMP at any time (apart from withdrawal of informed consent) will be required to complete the End of Treatment (EoT) [ ] a minimum of [ ] after the last dose of IMP and enter the [ ].

washout period. Subjects who withdraw from the study during Part 3 will undergo the [REDACTED] (End of Study [EoS]) assessments at [REDACTED] after their last visit.

The primary endpoint for efficacy will be ASAS20 at [REDACTED]. Secondary endpoints will include ASAS20 at [REDACTED], ASAS40 at [REDACTED]; and the proportion of subjects who require adjustment of background therapy. The PK and immunogenicity of tildrakizumab will also be evaluated.

All sites will have an independent assessor to conduct the assessments detailed in [REDACTED]. The independent assessor will not be involved in the care of subjects and will not discuss disease activity or the treatment with subjects or the Principal Investigator (PI)/designee responsible for performing other efficacy and safety evaluations.

An interim analysis (IA) will be performed for futility assessment after data from [REDACTED] randomized subjects become available at [REDACTED].

Following the last subject's [REDACTED], an IA will be conducted on all available data to evaluate the primary efficacy outcome.

A Data Safety Monitoring Board (DSMB) will be established for periodic review of safety data for this study, and a Clinical Adjudication Committee (CAC) will be established to evaluate cardiovascular events [REDACTED].

Central review of radiographs used for inclusion/exclusion (except chest X-rays for tuberculosis [TB] evaluation, where applicable) will be performed to ensure consistent assessment across sites. Scoring of MRI data collected throughout the study will be conducted by a central reader who will be blinded to the time sequence and subject treatment.

The EoS is defined as the last visit of the [REDACTED] of the last global subject.

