2.2 Secondary objectives

Parts 1 and 2

- To evaluate the efficacy of tildrakizumab in subjects with AS or nr-axSpA, as measured by the proportion of subjects achieving ASAS20 response criteria at [REDACTED], and ASAS40 response criteria at [REDACTED], and proportion of subjects who require adjustment of background therapy.
- To characterize the pharmacokinetics (PK) of tildrakizumab in subjects with AS or nr-axSpA.

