4.2 Secondary efficacy endpoints (up to [REDACTED])

The secondary efficacy endpoints of this study are:

Statistical Analysis Plan (SAP)

Parts 1 and 2

- The proportion of subjects who achieve ASAS20 at [REDACTED]
- The proportion of subjects who achieve ASAS40 at [REDACTED]

- The proportion of subjects who require adjustment of background therapy

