8.6 Efficacy analyses

8.6.1 Analysis methods

Analysis of proportions

The Cochran-Mantel-Haenszel (CMH) test, incorporating prior anti-TNF use as a stratification factor, will be used to compare response rates of response-type variables between the 200 mg tildrakizumab and placebo within AS and nr-axSpA separately. In addition, the Mantel-Haenszel common risk (the response rate) difference between 200 mg tildrakizumab and placebo and the 95% confidence interval (CI) will be estimated. Should assumptions per the Mantel-Fleiss criterion not be satisfied, the comparison will be based on a Fisher's exact test after collapsing across levels of the stratification factor. In this case, the response rate difference and CI will be based on a normal approximation without considering stratification.

Mixed model repeated measures analysis of continuous endpoints

A mixed model repeated measure (MMRM) analysis will be performed. The SAS procedure PROC MIXED will be used. The preferred model will include the fixed categorical effects of treatment, visit, treatment-by-visit interaction, and prior TNF use (yes/no), as well as the continuous fixed covariate of baseline value. An unstructured matrix for the within-subject error variance-covariance will be used. The denominator degrees of freedom will be calculated according to the Kenward-Roger method.

In case of non-convergence with the unstructured matrix, other within-subject error variance-covariance matrices, such compound symmetry (CS), will be considered.

The model will provide least-squares mean estimates, standard errors, two-sided 95% confidence intervals and p-values (where applicable) for mean change at all time points between treatments (tildrakizumab vs. placebo).

Statistical Analysis Plan (SAP)

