8.6.2 Analysis of primary efficacy endpoint

The primary efficacy variable is ASAS20 at [REDACTED] ASAS20 will be analysed with CMH test as described in [REDACTED] for AS and nr-axSpA cohorts separately. Early withdrawals and any subjects with ASAS20 undeterminable at [REDACTED] will be classified as non-responders. Subjects who fail to show minimal response to treatment (defined as [REDACTED] improvement from Baseline in total back pain or inflammation) at [REDACTED] may have their background medications adjusted according to the maximum permitted daily dose described in the protocol and continue in the study. Any subject requiring these adjustments will be counted as a non-responder for the primary analysis.

The sample SAS codes are:

[REDACTED]
[REDACTED]
[REDACTED]

To assess the robustness of the primary efficacy analysis, sensitivity analysis will be repeated with the PPAS.

Subgroup analysis will be performed for each of the following subgroup variables:

- Prior anti-TNF use (Yes/No)
- Baseline weight (≤ 90 kg, > 90 kg)
- Age (< 65 , ≥ 65)
- Gender
- Methotrexate use (Yes/No)

The sample SAS codes for anti_TNF subgroup analysis are:

[REDACTED]
[REDACTED]
[REDACTED]
[REDACTED]
[REDACTED]
[REDACTED]

Estimates of the difference between the treatment groups, along with the [REDACTED] (but no p-value needed), will be presented for each defined category of each subgroup variable.

Statistical Analysis Plan (SAP)

If sample size for a category of a subgroup factor is too small, the analysis for that subgroup may not be performed.

The primary purpose of the subgroup analyses is to check for consistency of results across factors of interest.

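### Adjustment of background therapy is a secondary endpoint in SAP 2.2 and 4.2, but its only assigned analysis is a descriptive Week 16 summary among the exploratory endpoints, with no between-arm estimate

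*SAP*

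**What the plan says.** SAP 2.2 includes the endpoint in the secondary efficacy objective: "and proportion of subjects who require adjustment of background therapy". SAP 4.2 lists it as a secondary efficacy endpoint, "The proportion of subjects who require adjustment of background therapy", under a heading for Parts 1 and 2 and without a time point. SAP 4.3, the exploratory list, does not contain it.

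SAP 8.6.3 gives one secondary endpoint a test: "Proportions in ASAS40 at Weeks 24 will be analyzed based on the CMH method described for ASAS20 in primary analysis". It makes ASAS20 and ASAS40 descriptive at later times and gives the reason: "Due to the placebo group switching to 200 mg tildrakizumab at" a visit that is blacked out. Adjustment of background therapy is not named.

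SAP 8.6.4, on exploratory endpoints, is where it reappears: "proportion of subjects who require adjustment of background therapy at Week 16 will be summarized with descriptive statistics". That section uses the FAS.

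SAP 8.6.1 says that the stratified CMH test "will be used to compare response rates of response-type variables between the 200 mg tildrakizumab and placebo", with a Mantel-Haenszel difference and 95% CI. SAP 8.6.2 links adjustment to the primary endpoint: "Any subject requiring these adjustments will be counted as a non-responder for the primary analysis".

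**The concern.** The SAP places one endpoint in two tiers and gives the listed secondary objective no comparison of the arms. A reader who turns to the secondary analyses finds nothing on it. A reader who turns to the exploratory section finds counts.

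The endpoint deserves an estimate for two reasons. It is a direct comparison of how often each randomised arm needed extra background treatment, made while the trial is still placebo-controlled. The same events also turn a subject into a non-responder in the primary analysis, so their frequency by arm is context that a reader of the ASAS20 result will want with its uncertainty attached.

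**Working it through.** **1. The SAP sections side by side**

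| SAP section | Tier | Time point | Method |
|---|---|---|---|
| 2.2 | Secondary objective | None (Parts 1 and 2) | – |
| 4.2 | Secondary endpoint | None (Parts 1 and 2) | – |
| 4.3 | Not listed as exploratory | – | – |
| 8.6.3 | Not mentioned | – | None |
| 8.6.4 | Among the exploratory endpoints | Week 16 | Descriptive, FAS |
| 10 | No change recorded | – | – |

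Redaction does not explain the gap in 8.6.3. The visible black-outs there are time points within sentences about ASAS endpoints or the placebo switch.

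**2. Does the stated reason for not comparing arms apply?** Protocol 9.1.1 has placebo subjects "who complete the Week 24 visit will continue to Part 2 and receive tildrakizumab". Week 16 precedes that visit, so the arms are still as randomised. Adjustments under the Week 16 provision can be compared up to Week 24.

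**3. Do other texts settle the method?**
- The synopsis of the supplied protocol (14 June 2017) evaluates binary secondary endpoints like the primary, which means a stratified CMH test with a risk difference.
- The separate documentation of statistical methods (16.1.9) says much the same for secondary and exploratory response-type endpoints. It names only ASAS measures, and it differs from SAP 8.6.4, which makes the exploratory ones descriptive.
- SAP 7.2.1 also lists only ASAS composites as response-type.

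These texts lean towards a comparison, but none assigns one to this endpoint by name.

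**4. Precision of the missing estimate.** SAP 5 plans about 45 subjects per arm in each cohort. The documents give no adjustment rates, so 10% to 40% is assumed. The half-width, ignoring stratification, is 1.96 × √{[p_T(1 − p_T) + p_P(1 − p_P)] / 45}, where T is tildrakizumab and P is placebo:
- 10% v 10%: 1.96 × √(0.18/45) = 12.4 points
- 10% v 30%: 1.96 × √(0.30/45) = 16.0 points
- 20% v 40%: 1.96 × √(0.40/45) = 18.5 points
- 40% v 40%: 1.96 × √(0.48/45) = 20.2 points

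SAP 10 refers to termination of the study. Fewer subjects than planned would widen these intervals.

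**5. Part 2.** Protocol 10.6 allows adjustment throughout Weeks 25 to 52. SAP 3.1 takes tildrakizumab subjects without ASAS20 off study drug at the end of Part 1, but carries placebo subjects forward whatever their response. At an assumed ASAS20 response of 40% to 60%, 45 × 0.4 = 18 to 45 × 0.6 = 27 tildrakizumab subjects remain, against up to 45 from placebo. The remaining tildrakizumab subjects are all responders, so Part 2 rates do not compare like with like.

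**The case against.** The strongest reply is that this is one sentence filed under the wrong heading. A secondary endpoint in this SAP need not be tested: ASAS20 at Week 52 is secondary in the supplied protocol, and under SAP 8.6.3 it is descriptive because placebo subjects have switched. SAP 8.1 requires summaries by treatment group, so counts per arm will exist and a crude difference can be worked out from them. The trial is Phase 2a and SAP 8.6.1.1 declares multiplicity not applicable. The intervals above are also wide enough to make a descriptive summary defensible.

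Much of this stands, and it is why the point is minor. It does not remove it. The reason that makes the Week 52 endpoint descriptive is absent at Week 16, and a crude difference is not the stratified one that the SAP uses elsewhere.

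A second reply is that SAP 8.6.4 may class adjustment as response-type, so that the CMH method in 8.6.1 applies. A black-out has removed the closing bracket in that sentence, and some doubt remains. The legible wording nevertheless assigns descriptive statistics to this endpoint, and the specific text should govern over the general one.

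A third is that the Parts 1 and 2 heading covers all the secondary items, and that Week 16 is simply the working definition. That is a fair reading, but SAP 4.2 should then say so.

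**Conclusion.** The mismatch within the SAP is real and minor. A listed secondary endpoint has no analysis in the secondary section, and no between-arm estimate is assigned to it in a period when a randomised comparison is available. The mismatch rests on legible text. The interval widths rest on the assumed rates and on the planned 45 per arm.

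Three stronger readings are tempting and not supported:
- **That the endpoint goes unreported, or was deliberately demoted from the protocol.** SAP 8.6.4 does require a summary. The SAP follows protocol V3.0 of 19 March 2018, which is not supplied, so no departure from it can be claimed.
- **That an interval for the adjustment difference would show how much of the ASAS20 difference comes from counting adjusted subjects as failures.** That shift is a_P·r_P − a_T·r_T, where a is the share adjusted and r is the share of those who would otherwise have responded. The proposed analysis estimates only a_P − a_T. For illustration, a = 20% in both arms with r = 30% on placebo and 10% on tildrakizumab gives no adjustment difference, yet a shift of 6 − 2 = 4 points. With a = 40% v 10% and r = 10% v 30%, placebo first, the adjustment difference is 30 points and the shift is 4 − 3 = 1 point. The documents give neither a nor r.
- **That any such shift can be judged against the 12% futility threshold.** That threshold applies to Week 16 ASAS20 in 30 subjects, not to the Week 24 primary difference.

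**What to change.** Move the endpoint from SAP 8.6.4 to 8.6.3 and state the following there:
- **Definition:** a recorded adjustment of background medication under the Week 16 minimal-response provision, up to Week 24. These are the events that make a subject a primary non-responder. The word recorded matters, because the provision says that medication may be adjusted, so meeting the criterion and being adjusted are different things.
- **Analysis:** FAS, each cohort separately, by the SAP 8.6.1 method. This is the CMH test stratified by prior anti-TNF use and the Mantel-Haenszel difference with 95% CI, with the existing fallback if the Mantel-Fleiss criterion fails.
- **Part 2 adjustments:** descriptive only, for the reason in step 5 of the working.

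Give SAP 4.2 the same definition and time window.

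The cost is one paragraph, written before unblinding, and one extra table from concomitant-medication data already collected. The drawback is a wide interval, which should be reported as an estimate and not read as evidence of no difference.

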2.3 Exploratory objectives

Parts 1 and 2

- To evaluate the efficacy of tildrakizumab in subjects with AS or Nr-axSpA, as measured by the proportion of subjects who achieve ASAS20 or ASAS40 at other measured time points.
- To evaluate the efficacy of tildrakizumab in subjects with AS or nr-axSpA, as measured by the proportion of subjects who achieve ASAS70 or ASAS5/6.
- To evaluate the efficacy of tildrakizumab in subjects with AS or nr-axSpA, as measured by the change from Baseline in ASAS components, Bath Ankylosing Spondylitis Disease Activity Index (BASDAI), Bath Ankylosing Spondylitis Metrology Index (BASMI), Bath Ankylosing Spondylitis Functional Index (BASFI), Ankylosing Spondylitis Quality of Life questionnaire (ASQoL), Visual Analog Scale (VAS) (total back pain and nocturnal pain score), Ankylosing Spondylitis Disease Activity Score (ASDAS) C-reactive protein (CRP), ASDAS erythrocyte sedimentation rate (ESR), Maastricht Ankylosing Spondylitis Enthesitis Score (MASES), short form 36 (SF-36), Functional Assessment of Chronic Illness Therapy (FACIT)-fatigue,

Statistical Analysis Plan (SAP)

high-sensitivity CRP (hs)CRP, SpondyloArthritis Research Consortium of Canada (SPARCC) magnetic resonance imaging (MRI) Index of Disease Activity of the Sacroiliac (SI) Joints, SPARCC MRI Index of Disease Activity of the Spine, and Modified Berlin Ankylosing Spondylitis Spine Magnetic Resonance Imaging Activity Score (ASspiMRI), swollen joint count of 44 joints (SJC44), and tender joint count of 46 joints (TJC46) at measured time points.

- To evaluate the tildrakizumab exposure/response relationship.

Part 3

- To assess the effect of investigational medicinal product (IMP) discontinuation on ASAS20, ASAS40, ASAS70, ASAS5/6, ASAS components, BASDAI, BASMI, BASFI, VAS (total back pain and nocturnal pain score), MASES, SF-36, FACIT-fatigue, TJC46, and SJC44 at measured time points.
- To evaluate immunogenicity following IMP discontinuation.
- To characterize the PK of tildrakizumab in subjects with AS or nr-axSpA following IMP discontinuation.

Statistical Analysis Plan (SAP)

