3.1 General study design

This is a randomized, multinational, double-blind, placebo-controlled, Phase 2a study. The study will consist of a Screening Period [REDACTED] Part 1, a double-blind, placebo-controlled period [REDACTED] Part 2, a [REDACTED] follow-up period [REDACTED] and Part 3, a [REDACTED] During the wash-out period, subjects will no longer receive tildrakizumab and will be treated according to the Investigators' discretion.

At least [REDACTED] subjects with active AS (Stage 1 of study) and 90 subjects with active nr-axSpA (Stage 2 of study) who satisfy the inclusion criteria and do not meet the exclusion criteria will be enrolled in this study. Approximately [REDACTED] subjects will be randomized into the Double-Blind treatment period.

The Study Flow Chart is presented in Figure 1.

Figure 1: Study Flow Chart

Statistical Analysis Plan (SAP)

Abbreviations: AS = ankylosing spondylitis; mg = milligram; nr-axSpA = non-radiographic axial spondyloarthritis; Wk = week

Subjects who fail to show minimal response to treatment (defined as [REDACTED] from Baseline in pain [assessed by total back pain VAS [REDACTED]] or inflammation [assessed using the last [REDACTED] stiffness assessments in the BASDAI]) at [REDACTED] in both stages of the study may have their background medications adjusted according to the maximum permitted daily dose and continue in the study.

Tildrakizumab subjects in both stages who achieve ASAS20 at [REDACTED] will receive treatment with [REDACTED] tildrakizumab [REDACTED] until [REDACTED]. Subjects receiving tildrakizumab during Part 1 who do not achieve ASAS20 at [REDACTED] will discontinue IMP treatment and enter the [REDACTED] washout period. Subjects randomized to receive placebo during Part 1 of both stages of the study who complete the [REDACTED] visit will continue to Part 2 and receive tildrakizumab 200 mg q4 weeks until [REDACTED] even if they do not achieve ASAS20. Subjects discontinued from IMP at any time (apart from withdrawal of informed consent) will be required to complete the EoT [REDACTED] assessment a minimum of [REDACTED] after the last dose of IMP and enter the [REDACTED] washout period. Subjects who withdraw from the study during Part 3 will undergo the [REDACTED] (End of Study [EoS]) assessments at least 4 weeks after their last visit.

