8 STATISTICAL METHODS

8.1 General Statistical Conventions

All statistical procedures will be completed using SAS version 9.4 or higher.

Unless otherwise stated, all statistical testing will be two-sided and will be performed using a significance (alpha) level of [REDACTED]

Summaries for AS or nr-axSpA will be presented separately. Summary statistics will also be presented by treatment group. Continuous variables will be summarized using descriptive statistics, including number of subjects (n), mean, median, standard deviation (SD), minimum and maximum. One additional decimal point for mean and median and 2 additional decimal points for SD will be used.

For categorical variables, summaries will include counts of subjects and percentages. Percentages will be rounded to one decimal place.

Two-sided 95% confidence intervals (CI) will be provided when relevant.

For summary purposes, baseline will be defined as the last available value prior to the date of first IMP administration; all summaries will be presented by treatment group, unless otherwise specified.

For reporting purpose, summary tables for efficacy variables and safety variables will be displayed by nominal visit as appropriate. Unscheduled assessments will not be included in the summary tables, but will be displayed in data listings.

All subject data, including those derived, will be presented in individual subject data listings. Unless otherwise stated, unscheduled visit results will be included in date/time chronological order, within patient listings only. All listings will be sorted by cohort, treatment group, subject number, date/time and visit. The treatment group as well as patient's sex and age will be stated on each listing. Unless otherwise stated, data listings will be based on all randomized subjects.

The treatment groups will be displayed in the format below in tables including Part 1 only:

- [REDACTED] Tildrakizumab
- Placebo

The treatment groups will be displayed in the format below for tables including Parts 2 and/or 3 and all listings:

- [REDACTED] Tildrakizumab
- Placebo → [REDACTED] Tildrakizumab

Statistical Analysis Plan (SAP)

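### Part 3 tables pool tildrakizumab subjects stopped for lack of ASAS20 with Part 2 completers, so that column cannot isolate the effect of stopping the drug

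*SAP*

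**What the plan says.** The first Part 3 objective in SAP 2.3 begins "To assess the effect of investigational medicinal product (IMP) discontinuation on ASAS20" and goes on to list the other ASAS measures, the Bath indices, pain, enthesitis, quality of life, fatigue and joint counts.

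SAP 3.1 lets subjects reach the washout by different routes. One group is described as "Subjects receiving tildrakizumab during Part 1 who do not achieve ASAS20 at" a visit whose number is redacted; these subjects stop IMP and go straight to washout. Placebo subjects who complete Part 1 move on to tildrakizumab in Part 2 whether or not they responded. Anyone else who stops IMP early, short of withdrawing consent, also enters washout. Part 2 completers may enter washout or, if judged likely to benefit, leave for the long-term extension. Treatment during washout is at the investigator's discretion.

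SAP 8.6.4 then summarises the Part 3 response rates by treatment group and states that the change-from-Baseline endpoints "during Weeks 53 to 72 will be summarized descriptively by treatment group". It adds that "there will be sub-groups of patients in Part 3 who either did or did not receive any new therapy for AS", to be analysed separately for ASAS20, ASAS40 and ASAS70. It closes with "All the exploratory analyses will be based on the FAS". Under SAP 8.1, Baseline is the last value before first dosing, and "summary tables for efficacy variables and safety variables will be displayed by nominal visit as appropriate".

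**The concern.** The effect of stopping a drug is a question about subjects who had some benefit when they stopped. A subject stopped for lacking ASAS20 has no ASAS20 response at that visit to lose. Pooling these subjects with Part 2 completers makes the Part 3 response rate depend on how many failed at the decision visit, as well as on what happened after stopping.

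This route exists only in the tildrakizumab arm, so the two columns differ in make-up by design. The new-therapy split does not replace route of entry: each of its two groups can still hold both non-responders and completers, and it does not cover ASAS5/6 or any continuous endpoint. Change from pre-dose Baseline also does not show directly what was lost after the last dose.

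At stake is whether the Part 3 tables can answer their own objective. A low pooled rate could be read as rapid loss of effect when it mainly reflects earlier non-response.

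**Working it through.** The plan gives no sample size or target figure for Part 3, so there is nothing to reproduce. The arm size, about 45 per arm in each cohort, is from SAP 5. The response, loss and extension rates below are assumptions, because the planning rates are redacted.

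**Step 1. Share of non-responders in the tildrakizumab column.** Assume no other dropout, no extension entry, and that responders at the decision visit complete Part 2. Share = non-responders / 45.

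- 40% ASAS20: 18 responders, 27 non-responders; 27/45 = 60%
- 50% (22.5, taken as 22): 23 non-responders; 23/45 = 51%
- 60%: 27 responders, 18 non-responders; 18/45 = 40%
- 70% (31.5, taken as 31): 14 non-responders; 14/45 = 31%

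**Step 2. Dilution of a real loss.** Take 22 completers and 23 non-responders. Assume 80% of completers respond at end of treatment (EoT) and 40% at end of study, and that the non-responders stay without ASAS20.

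- Pooled at EoT: 0.80 × 22 / 45 = 17.6/45 = 39.1%
- Pooled at end of study: 0.40 × 22 / 45 = 8.8/45 = 19.6%

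A 40-point fall among completers appears as a fall of just under 20 points.

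**Step 3. Extension entry and missing data.** Take 60% response: 27 completers (all still responders) and 18 non-responders.

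- Half of the completers enter the extension and every washout responder keeps the response: 13.5/(13.5 + 18) = 43% of those observed. In the FAS with missing counted as non-response, 13.5/45 = 30%.
- Nobody enters the extension and half of the responders lose response: 13.5/45 = 30%.

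The same 30% in the FAS can mean no loss or loss in half of the responders. SAP 7.2.1 sets missing response-type endpoints to non-response at all time points, but also says that missing values are in general not imputed in descriptive summaries. It is therefore not settled whether the Part 3 tables would show 43% or 30% in the first case.

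**Step 4. Timing.** The protocol synopsis gives a 20-week washout, and the protocol contents list places Part 3 at Weeks 56 to 72. The decision visit is redacted in SAP 3.1; Week 24 is an inference from the primary endpoint (Protocol 13.4.2) and the end of Part 1. On that inference washout ends at about 24 + 20 = Week 44, before Week 53. SAP 8.6.4 does not say whether such subjects enter the Weeks 53 to 72 summaries of continuous endpoints through nominal washout visits or fall outside them.

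**The case against.** The strongest reply is that this is a descriptive, exploratory part of a Phase 2a study. No test is made, no comparison of active drug with placebo is planned after the switch, and the primary analysis is untouched. Subject data and reasons for discontinuation are listed individually (SAP 8.1 and 8.3), so a reader could rebuild the routes by hand. The placebo-to-tildrakizumab column has no subjects stopped for non-response. All of this stands and limits the weight of the point. It does not supply a table that answers the objective.

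Four stronger readings are tempting, and the documents do not support them.

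- *That Part 3 is summarised by treatment group and nothing else.* The new-therapy split contradicts this for ASAS20, ASAS40 and ASAS70.
- *That the stopped subjects never responded.* The rule concerns ASAS20 at one visit; earlier response or partial improvement is possible, and such subjects can still worsen on continuous endpoints.
- *That new therapy could hide the loss altogether.* If 40% of the 23 non-responders respond on new therapy, the pooled rate at end of study is (8.8 + 9.2)/45 = 40% against 39% at EoT. For ASAS20 the planned split largely separates that case.
- *That the Weeks 53 to 72 window is wrong.* It is visible only for the continuous endpoints; the window for the response rates is redacted. Nominal-visit display makes it likely that early stoppers are mapped to the washout visits. The Part 3 schedule is redacted and the table templates are in a separate document. The defect is an unstated rule, not a demonstrated error.

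**Conclusion.** The point holds in a limited form. No summary described in the SAP separates tildrakizumab subjects stopped for lack of ASAS20 from Part 2 completers, or conditions on response when IMP stopped. The tildrakizumab column therefore cannot isolate the discontinuation effect that SAP 2.3 names.

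On the assumptions in steps 1 and 2, non-responders are roughly a third to three fifths of that column, and about half of a 40-point loss among completers is hidden. The exact share depends on redacted or unknown rates. Extension entry and the handling of missing responses can blur it further. The handling of early stoppers in the continuous summaries is unstated.

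SAP 10 drops only the PK and ADA analyses because of study termination, so these summaries remain planned. This is a worthwhile improvement to an exploratory analysis, with no bearing on the primary result.

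**What to change.** Amend SAP 8.6.4 and the table shells as follows.

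- Present Part 3 endpoints by treatment group and route of entry: stopped for lack of ASAS20 at the decision visit; other early IMP stop, with subjects who received only placebo shown apart; Part 2 completer.
- Use subjects who entered washout as the denominator, excluding those who left for the extension. State how data are handled for subjects who move to the extension from washout, which SAP 3.1 allows.
- Index visits by weeks since last IMP dose. SAP 8.7.1 already defines Part 3 TEAEs from the last dose, so efficacy and safety would then share an anchor and the mapping of early stoppers would be explicit.
- Add change from EoT beside change from Baseline.
- Report the proportion keeping ASAS20 among subjects in ASAS20 response at EoT, overall and before any new AS therapy.

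The cost is wording and programming on data already collected; no visit or treatment rule changes. The groups become smaller. The retained responders would be a selected group without a control, because completers judged to benefit may enter the extension. The tables should say so.
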